### **Sensitivity analyses**

Tipping point analysis based on the same MI method as applied to the primary analysis will be performed to examine the robustness of the results from the primary analysis. Patients who were randomized to sotagliflozin 400 mg group and had no HbA1c data at Week 26 will be given a penalty. The penalty will be gradually increased to evaluate at which level the conclusion of the analyses in terms of statistical significance is changed. The tipping point is the penalty level, at which the magnitude of efficacy reduction in patients without HbA1c data at Week 26 creates a shift in the treatment effect of sotagliflozin 400 mg from being statistically significantly better than placebo to a non-statistically significant effect. LS mean difference between sotagliflozin 400 mg and placebo and its associated p-value will be provided for each penalty level. The steps to perform the tipping point analysis are as follows:

1. Missing data will be imputed using the same MI method as applied to the primary analysis..

2. The imputed HbA1c value at Week 26 in the sotagliflozin 400 mg group will be penalized by adding a penalty  $\delta$  (eg,  $\delta = 0.1\%$ ) in each complete dataset..
3. Change from baseline at Week 26 in HbA1c will be analyzed using the same ANCOVA model as specified in the primary analysis in each complete dataset..
4. Results will be combined across complete datasets using Rubin's formula..
5. Steps 2 to 4 will be repeated with incremental penalty at  $\delta$  (ie,  $\delta, 2\delta, 3\delta, \dots$ ) until the p-value for treatment effect of sotagliflozin 400 mg compared to placebo estimated in Step 4 is  $>0.05$ .

The tipping point analysis will be performed on the ITT population. The tipping point analysis will be performed for the primary variable only if that variable (change from baseline to Week 26 in HbA1c comparing sotagliflozin 400 mg vs. placebo) is statistical significant at  $\alpha = 0.05$  (2-sided).

In addition to the tipping point analyses, if the retrieved dropout imputation is applied to the primary analysis, the analysis based on the washout imputation method (ie, the backup imputation method) will be presented as a sensitivity analysis.

Patients in this study have undergone sampling for plasma levels of sotagliflozin and its main active metabolite in order to perform population PK analysis. Patients may be identified as those who have no detectable levels of active study drug or metabolite in their samples (ie, Below Limit of Quantification or BLOQ). When sample analysis has been completed and the study has been unblinded, explanations for some of these patients may be found: known non-compliance or sampling occurring after treatment had been discontinued. In other cases, drug intake history relative to the randomization assignment may not be fully explained. The ITT-based analyses specified in this document provides for a conservative assessment of the efficacy data should patients have been subjected to these unexplained non-compliance findings or PK 'anomalies'. To provide a broader perspective on the impact of these apparent errors in compliance, additional sensitivity analyses of the primary efficacy endpoint and continuous efficacy endpoints may be conducted. The need to perform such analyses, their specifics, and results will be provided in the Clinical Study Report (CSR), if applicable. The analysis methods applied to the patient subpopulations defined by the occurrence of the PK anomalies (eg, exclusion of patients with PK anomalies from the ITT dataset) will include the ANCOVA model using the retrieved dropout and/or washout MI methods previously specified in this section.

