- E 16. Patient is unwilling to perform self-monitoring of blood glucose (SMBG) and complete the patient diary as required per protocol
- E 17. Patient insufficiently compliant during Run-in phase based upon tablet count (<80%) or in the opinion of the Investigator
- E 18. Patient with contraindication to sulfonylurea as per local labeling
- E 19. Patient with contraindication to metformin as per local labeling if the patient is taking sulfonylurea in combination with metformin
- E 20. Any country-related specific regulation that would prevent the patient from entering the study

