8.3.2 Randomization code breaking during the study

In case of an AE, the randomization code should only be broken in circumstances when knowledge of the IMP is required for treating the patient.

Code breaking can be performed at any time by using the proper module of the IRT and/or by calling any other phone number provided by the Sponsor for that purpose. Code breaking can be performed by a local study Investigator, sponsor physician or healthcare professional with direct responsibility for patient care. If the blind is broken, the Investigator should document the date, time of day, and reason for code breaking. The identity of the unblinded personnel, how the code was broken, and the treatment kit number should also be recorded. The Sponsor should also be informed. If the code is broken by the Investigator (or other medical doctor in an emergency situation), the patient must be withdrawn from IMP administration.

Randomization code breaking will also be performed during the analysis of the Pharmacokinetic plasma concentration samples. Only the Project manager and lead scientist at the Bioanalytical laboratory will have access to the randomization code to allow for the sorting of the sotagliflozin plasma samples. The Bioanalytical laboratory and responsible personnel will follow standard operating procedures to ensure the protection of the blind within the Sponsor's clinical team. The randomization code or the individual analytical results will not be disclosed to any clinical team personnel prior to the time of database lock.

Refer to [Section 10.5](#) for suspected unexpected serious adverse drug reaction unblinding by the Sponsor.

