9.3.1.1 Sampling time

Pre-dose PK samples at Weeks 4, 18, 26, 52, and 79 (Visits 5, 8, 9, 11, and 13, respectively) are to be drawn with the other laboratory assessments immediately before IMP administration.

Post-dose PK samples at Weeks 26 and 79 (Visits 9 and 13, respectively) should be drawn 1 hour 30 minutes after administration of IMP. See [Table 3](#) for the identification of samples.

Table 3 - Samples identification

Visit	Week	Relative to dosing	PK
Visit 5	Week 4	Pre-dose	P00
Visit 8	Week 18	Pre-dose	P01
Visit 9	Week 26	Pre-dose	P02
Visit 9	Week 26	Post-dose 1 h 30 min	P03
Visit 11	Week 52	Pre-dose	P04
Visit 13	Week 79	Pre-dose	P05
Visit 13	Week 79	Post-dose 1 h 30 min	P06

PK: pharmacokinetic.

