11.4.4 Analyses of pharmacokinetic variables

The PK endpoint is presented in [Section 9.3.1](#). Individual plasma concentrations of sotagliflozin and of its 3-O-glucuronide at nominal sampling times will be listed.

Concentration data will be summarized by visit and, if appropriate, within visit by nominal sampling times (pre-dose, 1 hour 30 minute post-dose), using descriptive statistics by N, geometric mean, coefficient of variation, median, minimum, and maximum at each visit/nominal sampling time point for sotagliflozin-treated patients.

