#### **2.1.5 Pharmacokinetic variables**

Pharmacokinetic variables include the plasma concentration of sotagliflozin and its 3-O-glucuronide metabolite in the sotagliflozin 400 mg group.

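### Does the optional exclusion of patients with PK anomalies from the ITT dataset call for a change to the SAP?

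*SAP*

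**What the plan says.** The Sensitivity analyses part of SAP 2.4.4.1 first specifies a tipping point analysis on the ITT population. It then adds the washout imputation analysis, for the case where retrieved-dropout imputation is primary. Neither removes a patient.

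A later paragraph deals with patients whose samples contain no measurable drug or metabolite. On timing it says: "When sample analysis has been completed and the study has been unblinded, explanations for some of these patients may be found". It names two possible explanations, known non-compliance and sampling after treatment had stopped, and treats the remaining cases as unexplained. Further analyses are permitted but not required: "The need to perform such analyses, their specifics, and results will be provided in the Clinical Study Report (CSR), if applicable". The ANCOVA and the imputation methods are fixed. The only example of a subpopulation is "exclusion of patients with PK anomalies from the ITT dataset".

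Other sections bear on which arm is affected. SAP 2.1.5 defines the PK variable as the "plasma concentration of sotagliflozin and its 3-O-glucuronide metabolite in the sotagliflozin 400 mg group". Protocol 11.4.4 summarizes concentrations "at each visit/nominal sampling time point for sotagliflozin-treated patients". Under Protocol 8.3.2 two named roles at the bioanalytical laboratory "will have access to the randomization code to allow for the sorting of the sotagliflozin plasma samples", and neither the code nor individual results reach the clinical team before database lock.

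The primary analysis uses all randomized patients whatever their compliance (SAP 2.3.1.1 and 2.4.4). The fixed sequence in SAP 2.4.4.4 contains no PK-anomaly analysis.

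**The concern.** A sensitivity analysis should test the assumptions behind an estimate while keeping its question. This exclusion changes the question. Undetectable drug cannot identify a placebo patient who skipped tablets, so the flag would take non-takers out of one arm and leave them in the other. What remains is a selected sotagliflozin group against all placebo patients.

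If those removed would have had worse HbA1c in any case, the comparison favours the drug. The paragraph also aims to show the impact of compliance errors, yet the gap between the exclusion result and the ITT result mixes two things, the dilution that has been removed and the selection that has been introduced.

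Timing adds to the worry. Explanations are sought after unblinding, and the need for the analysis and its details go to the CSR. A result chosen that way could be presented as evidence of robustness.

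**Working it through.** **Inputs from the documents.** SD 1.2, difference 0.6, 250 per arm, two-sided alpha 0.05 (Protocol 11.1, SAP 1.3).

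**Inputs assumed, because the documents do not give them.** f is the share of the sotagliflozin arm excluded. d is how much worse their HbA1c change would be without any drug effect. The main range is f 0.4% to 5% (1 to about 12 of 250) and d 0.2 to 0.6. f 10% is a stress case.

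**1. The plan's own figure.** SE = 1.2 × √(2/250) = 0.107. 0.6/0.107 = 5.59, and Φ(5.59 − 1.96) = 0.9999. This agrees with the stated 99% (SAP) and at least 99% (protocol).

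**2. ITT under non-compliance.** If takers gain 0.6 and non-takers gain nothing, the ITT difference is 0.6 × (1 − f): 0.588, 0.570 and 0.540 at f 2%, 5% and 10%. Power stays at 0.9989 or above, so the primary test does not depend on the PK analysis.

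**3. Bias of the exclusion when the drug does nothing.** Bias = f × d. SE = 1.2 × √(1/(250(1 − f)) + 1/250). With k = bias/SE, the two-sided error is Φ(−1.96 + k) + Φ(−1.96 − k).

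| f | excluded | SE | bias, d 0.2 | bias, d 0.6 | k, d 0.6 | error, d 0.6 |
|---|---|---|---|---|---|---|
| 0.4% | 1 | 0.107 | 0.0008 | 0.0024 | 0.02 | 0.050 |
| 2% | 5 | 0.108 | 0.004 | 0.012 | 0.11 | 0.051 |
| 5% | 12.5 | 0.109 | 0.010 | 0.030 | 0.28 | 0.059 |
| 10% | 25 | 0.110 | 0.020 | 0.060 | 0.54 | 0.085 |

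Simulation at f 10%, d 0.6 gave bias 0.060 and error 0.087. With d = 0 there is no bias. With d = −0.2 the bias is 0.0008 to 0.010 against the drug over f 0.4% to 5%. These figures are unadjusted. The planned ANCOVA includes baseline HbA1c and the strata, so only the part of d they do not explain would bias the result.

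**4. What the gap from ITT contains.** With no drug effect in those excluded, ITT = −0.6(1 − f) and exclusion = −0.6 − f × d. The gap is f × (0.6 + d), and the selection share of it is d/(0.6 + d): 25%, 40% and 50% at d 0.2, 0.4 and 0.6. At f 2%, d 0.4 this is −0.588 against −0.608. Of the 0.020 gap, 0.012 is removed dilution and 0.008 is bias.

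**5. Whether the obvious replacement is better.** A complier estimate keeps everyone and divides ITT by (1 − f). Its SE is 0.107/(1 − f): 0.110 at f 2% and 0.119 at f 10%, against 0.108 and 0.110 for exclusion. Suppose those flagged had half the drug effect. At f 2%, ITT is −(0.98 × 0.6 + 0.02 × 0.3) = −0.594 and the complier estimate is −0.594/0.98 = −0.606. At f 10% they are −0.570 and −0.633. Its bias is 0.3f/(1 − f), against f × d for exclusion. Exclusion is therefore the less biased when d is below 0.3/(1 − f), which is 0.31 at f 2% and 0.33 at f 10%.

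**The case for a change.** The strongest case for a change is that it would cost only words. Before unblinding, the SAP could say which samples and visits count and what counts as an explanation, and could call the exclusion exploratory. No assay result is needed to write that, so the blind is safe. Without it, a CSR could show a group chosen after unblinding under the same heading as the tipping point analysis.

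Part of this stands. By its stated criterion the exclusion would be one-sided, it is not a randomized comparison, and its gap from ITT cannot be read as the effect of compliance alone. A report that shows it should say so.

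The rest is weaker. One-sided action is an inference: the SAP names no arm, and its reference to drug intake relative to the randomization assignment could cover a placebo patient with detectable drug. Nor is the rule wholly open. The two named explanations rest on data recorded during the trial, namely compliance records (Protocol 8.7.1, SAP 2.4.3.2) and the last-dose date (SAP 2.5.3). Some unblinding is unavoidable, since an undetectable level is anomalous only once the patient is known to be on sotagliflozin. The schedule in Protocol 9.3.1.1 ("Pre-dose PK samples at Weeks 4, 18, 26, 52, and 79") already shows which samples precede each endpoint visit. A high f is made less likely by the entry rule that excludes a "Patient insufficiently compliant during Run-in phase based upon tablet count" below 80% and by retraining of poor compliers (Protocol 8.7.1). It would also require excluding every patient without detectable drug, whereas the text mostly reserves the word anomalies for unexplained cases.

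**Conclusion.** No change follows. The primary ITT comparison and the fixed sequence hold whether or not this analysis is run, and the SAP itself calls the ITT-based analyses conservative. For unexplained cases only, the bias is 0.001 to 0.03 HbA1c points, at most 0.28 SE, with its sign unknown. This rests on assumed f of 0.4% to 5% and d of 0.2 to 0.6. It reaches 0.06 only at f 10% with d 0.6.

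The missing operational rule is detail that analysts can supply from dosing records and sampling dates. An exploratory or post hoc label would alter no result. Replacing exclusion with a complier estimate exchanges one assumption for another, with a wider SE and more bias over the lower part of the assumed d range if those flagged had half the drug effect. Any such exclusion in the CSR should be read as a supplementary, non-randomized comparison.

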#### **Assessment of treatment effect by subgroup**

Descriptive analyses will be performed on the primary endpoint to summarize the treatment effects across subgroups defined by the following Baseline or Screening factors:

- Race (White, Black or African American, Asian, Other) (any race groups with fewer than 5 patients may be combined with "Other" category as appropriate).
- Ethnicity (Hispanic, Not Hispanic).
- Age group ( $<50, \geq 50$  to  $<65, \geq 65$  years) (any category with fewer than 5 patients may be combined with another category as appropriate).

- Gender (Male, Female).
- Baseline BMI level (<30, ≥30 kg/m^2).
- Baseline HbA1c (≤8.5%, >8.5%).
- Metformin use at Screening (Yes, No).
- Baseline mean SBP (<130 mmHg, ≥130 mmHg).
- Baseline eGFR (≥30 to <60 mL/min/1.73m^2 [Moderate decrease in GFR], ≥60 to <90 mL/min/1.73m^2 [Mild decrease in GFR], and ≥90 mL/min/1.73m^2 [Normal]).
- Duration of diabetes (<10, ≥10 years).
- Country.

The treatment effects (sotagliflozin 400 mg versus placebo) across the subgroups defined for each of these factors will be estimated for the change from Baseline to Week 26 in HbA1c in the ITT population, and using the same MI method as applied to the primary analysis. The ANCOVA model will include treatment groups (sotagliflozin 400 mg, placebo), randomization stratum of HbA1c (≤8.5%, >8.5%), randomization stratum of metformin use at Screening (Yes, No), randomization stratum of SBP (<130 mmHg, ≥130 mmHg), subgroup factor, treatment-by-subgroup factor, and country as fixed factors and baseline HbA1c values as a covariate. The adjusted estimates of treatment mean differences (sotagliflozin 400 mg versus placebo) with standard error (SE) and 95% CIs will be provided as appropriate across the subgroups. A graphical presentation of the results (ie, forest plot) will also be provided.

In the case that the subgroup factor is identical or similar to a randomization strata factor (eg, baseline HbA1c, metformin use at screening, or baseline mean SBP category), only the subgroup factor (as a single factor or an interaction term) will be included in the model in order to avoid the issue of collinearity in the analysis. The corresponding strata factor will not be included in the model.

#### **Summary statistics at scheduled visits**

Summary statistics (for screening value, baseline value, observed post-baseline value and its changes from baseline) at scheduled visits will be provided for each treatment group. The summary will include the number of observations, mean, SD, SE, minimum, median, and maximum. Graphical presentations will also be used to examine trends over time using mean values (±SE) and mean changes from baseline (±SE) at each of the scheduled visits.

Similar presentations will be provided excluding measurements after rescue therapy during the entire 79-week double-blind treatment period.

#### **2.4.4.2 Analyses of secondary efficacy endpoints**

For continuous secondary efficacy parameters with missing data at baseline, missing baseline data will be imputed using MI under the missing at random (MAR) assumption. Missing data at baseline will be imputed using regression method that includes randomization stratum of HbA1c

( $\leq 8.5\%$ ,  $> 8.5\%$ ), randomization stratum of metformin use at Screening (Yes, No), randomization stratum of SBP ( $< 130$  mmHg,  $\geq 130$  mmHg), and baseline value in the imputation model..

Each continuous secondary efficacy endpoint (Section 2.1.3.2) will be analyzed using a similar ANCOVA model including the measurements at baseline and endpoint (observed or imputed). The missing data at endpoint will be imputed by the retrieved dropouts if there are at least 5 patients in each study treatment group who discontinued but have the endpoint. Otherwise, the washout imputation method will be used according to the criterion described in Section 2.4.4.1. After the imputation, each of the complete datasets will be analyzed by an ANCOVA model.

The ANCOVA model will include treatment groups (sotagliflozin 400 mg, placebo), randomization stratum of HbA1c ( $\leq 8.5\%$ ,  $> 8.5\%$ ), randomization stratum of metformin use at Screening (Yes, No), randomization stratum of SBP ( $< 130$  mmHg,  $\geq 130$  mmHg), and country as fixed effects, and the corresponding baseline secondary endpoint value as a covariate. For the analysis of SBP in patients with baseline SBP  $\geq 130$  mmHg, the randomization stratum of SBP will not be included in the ANCOVA model. Results from each complete dataset will be combined using Rubin's formula to provide the adjusted mean change from Baseline to Week 26 (or Week 12 for SBP) for each treatment group, as well as the between-group difference (comparing sotagliflozin 400 mg versus placebo) and the 95% CI for the difference.

For all continuous secondary endpoints, summary statistics at scheduled visits will be provided for each treatment group. The summary will include the number of observations, mean, SD, SE, minimum, median, and maximum. Graphical presentations will also be used to examine trends over time using mean values ( $\pm$ SE) and mean changes from baseline ( $\pm$ SE) at each of the scheduled visits. In addition, SBP will be summarized descriptively at each visit for those patients with baseline SBP  $\geq 140$  mmHg.

The categorical secondary efficacy variables of HbA1c  $< 6.5\%$ ,  $< 7\%$  at Week 26 will be analyzed respectively using a Cochran-Mantel-Haenszel (CMH) method stratified by randomization stratum of HbA1c ( $\leq 8.5\%$ ,  $> 8.5\%$ ), randomization stratum of metformin use at Screening (Yes, No), and randomization stratum of SBP ( $< 130$  mmHg,  $\geq 130$  mmHg). The proportion in each treatment group will be provided, as well as the difference of proportions between sotagliflozin 400 mg and placebo with the associated 2-sided 95% CI. For HbA1c responders at Week 26 ( $< 6.5\%$ ,  $< 7\%$  respectively), all values at Week 26 will be used to determine whether a patient is a responder or not, even if they are measured after IMP discontinuation or rescue medication use. Patients who have no HbA1c measurement at Week 26 will be treated as non-responders. Summary tables and graphs will also be provided by treatment group at scheduled visits.

For between-group comparison, a sensitivity analysis will be performed respectively for HbA1c  $< 6.5\%$  responder analysis by excluding patients whose HbA1c values at baseline are  $< 6.5\%$ , and for HbA1c  $< 7\%$  responder analysis by excluding patients whose HbA1c values at baseline are  $< 7\%$  using the same CMH test mentioned above. Similarly, by-visit summary may also be provided excluding those patients.

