11 STATISTICAL CONSIDERATIONS

11.1 DETERMINATION OF SAMPLE SIZE

The sample size/power calculations are based on the primary variable, change from Baseline to Week 26 in HbA1c. Assuming a common standard deviation (SD) of 1.2% and using a 2-sided test at a 0.05 α -level, 250 patients per arm will have at least 99% power to detect a treatment difference of 0.6% in mean HbA1c change from Baseline to Week 26 between sotagliflozin 400 mg and placebo.

The number of patients taking a sulfonylurea and metformin will be limited to 330 patients, to ensure sufficient numbers of sulfonylurea monotherapy patients.

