11.4.2.2 Analyses of secondary efficacy endpoints

The secondary endpoints (see [Section 9.1.2](#)) will be analyzed using a similar approach to the primary efficacy endpoint with missing values imputed by control-based multiple imputation method under the missing not at random framework.

- For placebo patients, missing data will be imputed based on the placebo group data

- For patients in the sotagliflozin group, missing data will be imputed as if the patients were on placebo group throughout the study

For each of the continuous secondary endpoints, each of the complete datasets will be analyzed by an ANCOVA model with treatment groups (sotagliflozin, placebo), randomization stratum of HbA1c ($\leq 8.5\%$, $> 8.5\%$), randomization stratum of metformin use at Screening (Yes, No), randomization stratum of SBP (< 130 mmHg, ≥ 130 mmHg), and country as fixed effects, and Baseline secondary endpoint value as a covariate. For the analysis of SBP in patients with Baseline SBP ≥ 130 mmHg, the randomization stratum of SBP will not be included in the ANCOVA model. Results from each complete dataset will be combined to provide the adjusted mean change from Baseline to Week 26 (or Week 12 for SBP) for each treatment group, as well as the between-group difference (comparing sotagliflozin versus placebo) and the 95% CI for the difference.

The categorical secondary efficacy variables of HbA1c $< 6.5\%$, $< 7\%$ at Week 26 will be analyzed using a Cochran-Mantel-Haenszel method stratified by randomization stratum of HbA1c ($\leq 8.5\%$, $> 8.5\%$), randomization stratum of metformin use at Screening (Yes, No), and randomization stratum of SBP (< 130 mmHg, ≥ 130 mmHg). The proportion in each treatment group will be provided, as well as the difference of proportions between sotagliflozin and placebo with associated 2-sided 95% CI. For HbA1c responders at Week 26 ($< 6.5\%$, $< 7\%$ respectively), all values at Week 26 will be used to determine whether a patient is a responder or not, even if they are measured after IMP discontinuation or rescue medication use. Patients who have no HbA1c measurement at Week 26 will be treated as non-responders.

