## 1 OVERVIEW AND INVESTIGATIONAL PLAN

### 1.1 STUDY DESIGN AND RANDOMIZATION

This is a Phase 3, multicenter and multinational, randomized, double-blind, placebo-controlled, parallel-group study. Patients will be randomly assigned 1:1 to the following 2 treatment groups

- Sotagliflozin 400 mg.
- Placebo.

All patients will have a Screening Period comprised of an up to 2-week Screening Phase and a 2-week, single-blind placebo Run-in Phase prior to randomization. Following randomization, patients will have a 26-week, double-blind Core Treatment Period, a 53-week double-blind Extension Period, and a 2-week post-treatment Follow-up period to collect safety information (patients who prematurely discontinue the study treatment are expected to continue in the study).

At the end of the screening period, eligible patients will be centrally randomized (using permuted block randomization schedule) via an Interactive Response Technology (IRT). The randomization will be stratified by

- Hemoglobin A1c (HbA1c) at Screening ( $\leq 8.5\%$ ,  $> 8.5\%$ ).
- Metformin use at Screening (Yes, No).
- Systolic blood pressure (SBP) at Screening ( $< 130$  mmHg,  $\geq 130$  mmHg).

It is anticipated to randomize a total of approximately 500 patients.

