### 1.3 DETERMINATION OF SAMPLE SIZE

The sample size/power calculations are based on the primary variable, change from Baseline to Week 26 in HbA1c. Assuming a common standard deviation (SD) of 1.2% and using a 2-sided test at a 0.05  $\alpha$ -level, 250 patients per arm will have 99% power to detect a treatment difference of 0.6% in mean HbA1c change from Baseline to Week 26 between sotagliflozin 400 mg and placebo.

The number of patients taking a sulfonylurea and metformin will be limited to 330 patients, to ensure sufficient numbers of sulfonylurea monotherapy patients.

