For patients in the sotagliflozin 400 mg group with missing data at Week 26 (or Week 12 for SBP), their missing values will be imputed using observed baseline and the observed primary endpoint data from placebo completers; no intermittent values from either placebo or the active treatment groups will be used.

For placebo patients, missing data will be imputed based on the placebo group data. Intermittent observed values will be used while imputing missing values at Week 26 (or Week 12 for SBP). In cases that a non-monotone missing data pattern occurs at the intermediate visits, these data points will be first imputed in the placebo group using the Markov Chain Monte Carlo (MCMC) option in PROC MI to achieve a monotone missing pattern for all placebo patients. The Week 26 (or Week 12 for SBP) endpoint values will be subsequently imputed from the multiple copies of the original dataset where each copy will have a monotone missing pattern.

The imputation models for the washout MI method will include the randomization strata and the corresponding baseline value. Missing data will be imputed using the regression method.

In cases of non-convergence during the imputations, especially for the MCMC application in the placebo non-monotone datasets, graphical measures (eg, trace and autocorrelation plots) will be used to identify the offending variable and once detected, that variable(s) will be dropped from the model and the imputations will be re-run. These re-run models will use the same seed number and number of imputations as used in the original models.

Using either imputation method, missing endpoint data will be imputed 2000 times to generate multiple data sets with complete data. Other details of the imputation procedures such as the seed number and sort ordering are specified in the SAS programs. The HbA1c change from baseline to Week 26 (or Week 12 for SBP) will be derived from observed and imputed HbA1c values at Week 26 (or Week 12 for SBP).

Each of the completed datasets after the imputation will be analyzed using the Analysis of Covariance (ANCOVA) model with treatment groups (sotagliflozin 400 mg, placebo), randomization stratum of HbA1c ( $\leq 8.5\%$ ,  $> 8.5\%$ ), randomization stratum of metformin use at Screening (Yes, No), randomization stratum of SBP ( $< 130$  mmHg,  $\geq 130$  mmHg), and country as fixed factors, and baseline value of the efficacy endpoint as a covariate.

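### Adding continuous baseline HbA1c to the HbA1c responder analyses would be a small, cheap gain in precision over a valid CMH test

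*SAP*

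**What the plan says.** SAP 2.4.4.2 (Analyses of secondary efficacy endpoints) says that reaching HbA1c <6.5% or <7% at Week 26 "will be analyzed respectively using a Cochran-Mantel-Haenszel (CMH) method stratified by randomization stratum of HbA1c". Metformin use and systolic pressure, both at Screening, complete the strata. Protocol 11.4.2.2 has the same test: these variables "will be analyzed using a Cochran-Mantel-Haenszel method stratified by randomization stratum of HbA1c". Both documents report the difference in proportions with a 95% CI, and both count a missing Week 26 HbA1c as non-response.

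For HbA1c change, the ANCOVA in SAP 2.4.4.1 (Primary analysis) carries the same three strata, "and country as fixed factors, and baseline value of the efficacy endpoint as a covariate". Continuous baseline HbA1c does not enter the responder test. It appears there only as an exclusion rule, in an SAP sensitivity analysis that drops patients already below the threshold at baseline.

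SAP 2.4.4.4 and Protocol 11.4.2.4 place HbA1c <7.0% fifth and last among the secondary endpoints in the fixed sequence. HbA1c <6.5% is not listed and has no multiplicity control.

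**The concern.** A patient's chance of falling below 7.0% depends in part on where the patient starts. Exclusion E 21 (Protocol 7.2.2) confines screening HbA1c to 7–10%, and the split at 8.5% is coarse over that range. A patient at 7.1% needs a fall of just over 0.1 point to reach <7.0%. A patient at 8.5% needs more than 1.5 points. Both sit in the ≤8.5% stratum, and the planned treatment difference is only 0.6. The stratum also uses the screening value, not the later baseline value.

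The prognostic variation left inside each stratum widens the interval for the risk difference and costs some power. The baseline value that would recover part of it is already collected and already used in the ANCOVA. At stake is precision, not bias or type I error.

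**Working it through.** **1. The plan's own figure.** Inputs from SAP 1.3 and 1.1: "Assuming a common standard deviation (SD) of 1.2% and using a 2-sided test at a 0.05" level; "250 patients per arm will have 99% power to detect a treatment difference of 0.6" (in % HbA1c); allocation 1:1.

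- Power = Φ(δ/[σ√(2/n)] − 1.960). Here 0.6/(1.2 × √(2/250)) = 0.6/0.1073 = 5.59, and 5.59 − 1.96 = 3.63, so power is 99.99%. The noncentral t (498 df) gives the same.
- n per arm for 99% power = 2(1.960 + 2.326)²(1.2/0.6)² = 2 × 18.37 × 4 ≈ 147.

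The stated 99% (at least 99% in Protocol 11.1) therefore holds. The documents give no power, responder rate, baseline HbA1c distribution or baseline-outcome correlation for the responder endpoints, so the rest is simulation under assumptions.

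**2. Assumptions.** Screening HbA1c is normal, mean/SD 8.2/0.8 or 8.4/0.9, truncated to 7–10%. Screening-to-baseline noise SD is 0–0.4. The slope of Week 26 on baseline HbA1c is 0.4–1.0. SD of change is 1.2 (the plan's) or 0.9. The effect is 0.6 (the plan's) or smaller. Placebo change is about −0.2 to −0.3. Country effects and missing data are left out here.

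**3. Two measures of loss.**

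- Variance-based: 1 − (1 − R² with strata and continuous baseline)/(1 − R² with the HbA1c stratum only), from 1,000,000 patients per scenario.
- Trial-based: 1 − (mean CMH z / mean logistic z)², from 3,000–4,000 trials of 500 patients in 2 × 2 × 2 = 8 strata.

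Worked examples: SD 0.9, slope 1.0 gives 1 − (1 − 0.232)/(1 − 0.104) = 14.3%. SD 1.2, slope 1.0, effect 0.6 gives 1 − (3.765/3.898)² = 6.7%.

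**4. Results for HbA1c <7.0%** (screening 8.2/0.8, noise SD 0.3; power is CMH → logistic with continuous baseline):

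| SD of change | Slope | Variance-based loss | Trial-based loss, effect 0.6 | Power, effect 0.6 | Power, effect 0.4 |
|---|---|---|---|---|---|
| 1.2 | 0.4 | 1.4%* | about 0 | 99.3 → 99.3% | 83.1 → 83.4% |
| 1.2 | 0.6 | 3.5% | 1.3% | 98.8 → 99.0% | 79.0 → 80.6% |
| 1.2 | 0.8 | 5.8% | 3.7% | 97.9 → 98.1% | 73.8 → 76.7% |
| 1.2 | 1.0 | 8.6% | 6.7% | 96.9 → 97.6% | 71.5 → 75.3% |
| 0.9 | 0.8 | 9.9% | 4.9% | 99.7 → 99.8% | 88.5 → 90.9% |
| 0.9 | 1.0 | 14.3% | 9.1% | 99.7 → 100.0% | 85.2 → 90.2% |

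*Lowest value over the scenarios run at this slope.

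For HbA1c <6.5%, the variance-based loss ran from 1.1% to 10.8% over both SDs.

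**5. Check on the risk-difference scale.** The CMH-weighted and logistic-standardised risk differences were compared in 500-patient trials with an assumed 8% missing, counted as non-response. The standardised estimate had the lower variance in all 24 scenarios, by about 1–7% at SD 1.2 and 1–12% at SD 0.9. Point estimates agreed and type I error was about 5–6%. A further set at SD 1.2 and effect 0.6, with 0–10% missing, gave about 4–5% at slope 0.7 and 6–11% at slope 1.0, with about 2 points of power gained at slope 1.0. The upper end of any range is therefore approximate.

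**6. Scale in planning terms.** Power = Φ{[Δ − 1.96√(2p̄q̄/n)]/√[(p₀q₀ + p₁q₁)/n]}. For 20% v 35% with n = 250: (0.15 − 1.96 × 0.0399)/0.0394 = 1.82, so 96.6%. If 6–10% of the information is recovered (n = 250/0.94 to 250/0.90), power is 97.4–97.9%. For 17% v 34% it moves from 99.3% to 99.5–99.6%. For 15% v 25% it moves from 80.0% to 82.4–84.0%. These rates are illustrative.

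**The case against.** The case for leaving the plan alone is good. CMH on the randomisation factors needs no outcome model, controls type I error, matches the stratified design, and is prespecified alike in both documents. The estimated difference in proportions is not biased. The same laboratory variable already receives full baseline adjustment as the primary endpoint. HbA1c <7.0% is the last step, so no later test depends on it, and at the planned effect its power is near the ceiling either way. A model-based replacement also brings choices that CMH avoids: a functional form, a variance estimator for the standardised difference, and a rule for non-convergence or few events. All of this stands. It limits the point to a minor improvement and dictates what the fix must specify, but it does not remove the gain.

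Two stronger readings are tempting. A reader might infer a fixed loss of about 6–10% on a confirmatory endpoint. The documents do not support this, because no baseline-outcome slope is given. At the plan's SD of 1.2% most scenarios gave less, and 6–10% needs a slope of about 0.8–1.0 or a smaller SD. A reader might also infer that treating HbA1c one way in the ANCOVA and another in the responder test is an error or an inconsistency. It is a choice between two valid methods.

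**Conclusion.** The point holds as a cheap improvement, not as an error. The responder analyses leave out a prognostic covariate that the ANCOVA already uses. The cost is roughly 1–9% of the information at an SD of change of 1.2%, and up to about 14% at 0.9%. For HbA1c <7.0%, the only responder endpoint under multiplicity control, the power gain is about 0–2 points at the planned 0.6% effect and up to about 5 points if the effect is 0.4%. These figures rest on the assumed HbA1c distribution, screening-to-baseline noise, slope and SD set out above. The direction was consistent wherever the variances of the two risk differences were compared, but the size is not a property of the plan. HbA1c <6.5% would gain in precision only, since no controlled test attaches to it.

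**What to change.** Before unblinding, prespecify the following for both responder endpoints:

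- A logistic model with treatment, continuous baseline HbA1c (functional form stated) and the three randomisation strata.
- The standardised (marginal) risk difference, so that the reported difference in proportions is kept and is not replaced by a conditional odds ratio.
- A named variance estimator, such as the delta method allowing for random covariates, or a bootstrap, with the 95% CI and Wald test based on it.
- A fallback to the current CMH analysis if the model does not converge or events are sparse, which is most likely for <6.5%.
- CMH retained as a sensitivity analysis, and the non-responder rule unchanged.

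The same change is needed in SAP 2.4.4.2, SAP Appendix C, Protocol 11.4.2.2 and the statistical section of the protocol's Clinical Trial Summary, so that the named test for HbA1c <7.0% agrees everywhere. The cost is a small amendment to both documents, a modest change of program, and a somewhat less familiar, model-based method. No new data are needed. If the sponsor prefers to keep CMH as the confirmatory test, the same model can be added as a prespecified supportive analysis. That improves the reported precision but not the power of the sequence step.
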